The Safety and Efficacy of the Transnasal Humidified Rapid-Insufflation Ventilatory Exchange (THRIVE) for Short Diagnostic Bronchoscopy Procedures

Statistical Analysis Plan

NCT03086408

June 9, 2020

Means and standard deviations were calculated for each of the patient characteristics. The statistical significance of differences between THRIVE and non-THRIVE patients was assessed using unpaired two sample Student's t-test with 95% confidence interval for all patient characteristics, without adjusting for multiple comparisons. For patients' gender, a chi-square test was used.

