The Safety and Efficacy of the Transnasal Humidified Rapid-Insufflation Ventilatory Exchange (THRIVE) for Short Diagnostic Bronchoscopy Procedures

Study Protocol
NCT03086408

February 21, 2017

STUDY OBJECTIVES

1. DETERMINING THE SAFETY AND EFFICACY OF THRIVE FOR SHORT DIAGNOSTIC BRONCHOSCOPIC PROCEDURES.

THRIVE should improve glottic and tracheal exposure, operating conditions, decrease surgical time, and potentially lead to better patient outcomes. The safety of THRIVE for short diagnostic bronchoscopy has not been formally investigated, and will be explored in this study. With the patient anesthetized, apneic, and adequately oxygenated with THRIVE, the build-up of carbon dioxide in patient's blood (PaCO₂) and ensuing acute hypercapnic acidosis will be the main factors limiting the duration of THRIVE administration. At present, the rate of PaCO₂ rise with THRIVE has not been directly investigated, but is suggested to be 1.1 mm Hg per minute. It is expected that the short duration of diagnostic bronchoscopy procedures explored in this study will not lead to substantial rise of PaCO₂. The PaCO₂ rise to 70 mm Hg is considered a safe level for moderate hypercapnia in patients without significant comorbidities (see Exclusion Criteria).

2. DETERMINING POSSIBLE BENEFICIAL EFFECT OF THRIVE ON IMMEDIATE POSTOPERATIVE RECOVERY, OPIOD CONSUMPTION, AND FUNCTIONAL RECOVERY.

INCLUSION CRITERIA

Subjects presenting for short diagnostic bronchoscopy procedures under general anesthesia, including patients after bone marrow transplant (BMT).

EXCLUSION CRITERIA

1. Patients with significantly decreased myocardial function.
2. Patients with cardiac arrhythmias.
3. Patients with significant peripheral vascular disease.

STUDY PROTOCOL: THRIVE AND DIAGNOSTIC BRONCHOSCOPY

2

4. Patients with known significant cerebrovascular disease.
5. Patients with significant renal insufficiency.
6. Patients with electrolyte (K+, Ca++) abnormalities.
7. Patients with increased intracranial pressure or reduced intracranial compliance.
8. Patients with skull base defects.
9. Patients with pulmonary hypertension.
10. Immunocompromised patients.
11. Patients with significant chronic lung diseases.
12. Morbidly obese patients.
13. Patients with severe and poorly controlled gastsroesophageal reflux disease.
14. Patients with hiatal hernia and full stomach patients.
15. Patient's refusal to participate in the study.
16. Patients who do not understand English or mentally handicapped.

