17. Pregnant or breastfeeding patients.
18. "BMT patients with SpO2 < 90% on supplemental nasal oxygen up to 6 l/min, or those requiring non-rebreather mask to keep SpO2 > 90% will be excluded from the study."

PROTOCOL AT A GLANCE AND STUDY END-POINTS

1. Patients will be randomly assigned to either THRIVE or ETT/SGA (control group).
2. Anesthetic management is standardized for both groups.
3. Study end-points: per data collection sheet.

OPERATING ROOM PREPARATION

1. All drugs, airway supplies, eye tape, per routine.
2. 8.0 MLT ETT and SGA (i-Gel).
3. Precut large Tegaderm for securing ETT to the chin in left corner of mouth.
4. Four channel Alaris pump with:
 - a. NS carrier at 50 ml/hr
 - b. Propofol drip
 - c. Remifentanil drip
5. 20 ml NS syringe in line for chasing the induction and IVP drugs intraop. Please minimize IVF beyond 10 ml/kg total due to high incidence of urinary retention in male patients.
6. Working PNS with pads (make sure the battery is fresh).
7. Sedline or BIS.

STUDY PROTOCOL: THRIVE AND DIAGNOSTIC BRONCHOSCOPY

	THRIVE GROUP	CONTROL GROUP
PREOP and PREMEDICATION	
 • Obtain (check for) patient's consent. • Randomize the patient to either THRIVE or CONTROL group. • Obtain preop QoR15. • Peripheral IV, 20 g. • Midazolam 0.007 mg/kg incremental doses to achieve sufficient anxiolysis, not to exceed 0.025 mg/kg total dose. For elderly patients (70-80 y.o), limit total dose of Midazolam to 0.5 mg. 	
PRE-INDUCTION:	
Place standard ASA monitors, Sedline (BIS), and peripheral nerve stimulator (TOF ulnar nerve)
 
 • Apply THRIVE (FiO₂ 1.0) at 30 l/min. • Make sure the patient's head is elevated 30-40° (table in BACK UP position, not reverse Trendelenburg). 	
Preoxygenate.
 
 • IV fluid loading completed: 5 ml/kg. • IV Glycopyrrolate 0.2 mg if HR ≤ 50 bpm for elderly patients (70-80 y.o.). • Assure all bronchoscopy supplies are ready for immediate use in THRIVE group. • Both anesthesia and surgical time-outs completed.
INDUCTION	
 • IV Remifentanil 1 mcg/kg, Propofol 2mg/kg IV, Rocuronium 0. 6mg/kg IV. • Additional Remifentanil 0.5 mcg/kg and/or Propofol 0.5 mg/kg IV boluses, as required per hemodynamic responses and Sedline/BIS readings. 	

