	
 • Turn THRIVE to 70 l/min. • Maintain jaw thrust, with oral airway as necessary, throughout the procedure. 	
 • Mask ventilation as required. • Place SGA or ETT.
MAINTENANCE	
 • TIVA + THRIVE (FiO₂ 1.0) at 70 l/min. • NBP q 5 min, unless indicated more frequently. 	
 • TIVA + O₂:Air; FiO₂ = 0.5 or higher as required • NBP q 5 min, unless indicated more frequently.

STUDY PROTOCOL: THRIVE AND DIAGNOSTIC BRONCHOSCOPY

5

	
• If $\text{SpO}_2 < 90\%$, or ventricular arrhythmias, discuss with surgeon converting to either SGA or ETT.• If surgical duration more than 30 min, consider converting to either SGA or ETT. 
• Mechanical ventilation to normocapnia: EtCO_2 35-40 mmHg.• $\text{Vt} 6-8 \text{ ml/kg}$ of predicted body weight (PBW), PEEP 5 cmH₂O.• PBW Males = $50 + 2.3 (\text{Height}'' - 60)$• PBW Females = $45.5 + 2.3 (\text{Height}'' - 60)$

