STANDARDIZED POSTOP ORDERS	
• IV Fentanyl 25 mcg boluses q 5 min prn VAS ≥ 4, total dose 250 mcg.• PO Hydrocodone-acetaminophen (NORCO) 5-325 mg, 1 tab prn VAS ≥ 4, may repeat x 1.• If allergic to NORCO, Oxycodone-acetaminophen (PERCOCET) 5-325 mg, 1 tab prn VAS ≥ 4, may repeat x 1.• IV Demerol 10 mg for shivering only, may repeat x 1.• Treatment of PONV:
○ Zofran 8 mg IV x 1○ If no effect, and no contraindications, add IV Promethazine 12.5 mg x 1
PACU DATA COLLECTION	
• Obtain PACU data collection sheet and QoR15.
QUESTIONNAIRES and DIARIES	
• Pre- and post-procedural QoR15 questionnaires and post-procedural home diaries will be given to the patients. The BMT patients will receive QoR15 questionnaires, but will not keep the home diaries.

STUDY PROTOCOL: THRIVE AND DIAGNOSTIC BRONCHOSCOPY

7

THRIVE PROTOCOL	
PREOP	
• Randomize patient to THRIVE or ETT group.
PREINDUCTION	
• Start THRIVE @ 30 l/min immediately, before applying other OR monitors.• Maintain patient's head elevated 30-40°, with table in BACK UP, not reverse Trendelenburg position.
INDUCTION	
• THRIVE @ 70 l/min.• Place an oral intubating airway and maintain a jaw thrust for introduction of the fiberoptic scope by surgeon.
MAINTENANCE	
• Maintain THRIVE @ 70 l/min.• Maintain jaw thrust with the intubating oral airway in place for the duration of the procedure.• If surgery prolonged (over 30 min), consider converting to either SGA or ETT.
EMERGENCE	
• Maintain THRIVE at 70 l/min with jaw thrust ± oral airway as required, until return of spontaneous ventilation and consciousness.

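### Could a THRIVE patient converted to SGA or ETT be counted as non-THRIVE in the analysis?

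*SAP*

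**What the plan says.** The protocol names the comparison group more than once. Item 1 of Protocol at a Glance and Study End-points reads "Patients will be randomly assigned to either THRIVE or ETT/SGA (control group"), and the main study table then randomises to THRIVE or control under two columns headed that way. The preop row of the one-page THRIVE Protocol table instead says "Randomize patient to THRIVE or ETT group", leaving out the SGA. The control column at induction says "Place SGA or ETT".

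The maintenance row of the main table foresees that THRIVE may be abandoned. For SpO2 below 90% "or ventricular arrhythmias, discuss with surgeon converting to either SGA or ETT"; and "If surgical duration more than 30 min, consider converting to either SGA or ETT". The THRIVE Protocol table repeats the duration rule: "If surgery prolonged (over 30 min), consider converting to either SGA or ETT".

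The SAP is a single paragraph. Its only comparison is of "differences between THRIVE and non-THRIVE patients was assessed using unpaired two sample Student's t-test with 95% confidence interval for all patient characteristics", with a chi-square test for gender. It mentions no analysis set and no conversions.

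**The concern.** Conversion moves a THRIVE patient onto the devices used in the control arm. Such a patient is THRIVE by assignment but finishes on SGA or ETT. A literal-minded reader of the SAP's non-THRIVE label could place that patient on either side, and nothing written in the SAP settles it.

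The stake is the first objective, where the protocol says "The safety of THRIVE for short diagnostic bronchoscopy has not been formally investigated, and will be explored in this study". Low saturation is itself a trigger for discussing conversion, so every patient converted for that reason has already had the event. Moving those patients to the comparator would charge THRIVE's events to the controls. Dropping them would erase the events. Either error favours THRIVE on the question the trial was set up to answer.

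**Working it through.** **No stated figure to reproduce.** The documents give no sample size, event rate, allocation ratio or conversion count, and end-points are deferred to a data collection sheet that was not supplied. The check therefore has two parts: how large the distortion would be under a wrong grouping, and whether the documents lead anyone to that grouping.

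**Size under a wrong grouping.** Assume equal arms and conversion only for SpO2 below 90%. Let f be the share of the THRIVE arm with the event, c the share of the control arm, and s the share of the THRIVE patients with the event who are converted. All three are assumptions.

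- By randomised arm: f - c
- By final airway: f(1-s)/(1-fs) - (c+fs)/(1+fs)
- Converted patients dropped: f(1-s)/(1-fs) - c

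| f | c | s | By arm | By airway | Dropped |
|---|---|---|---|---|---|
| 10% | 0 | 0 | +10.0 | +10.0 | +10.0 |
| 10% | 0 | 50% | +10.0 | 0.05/0.95 - 0.05/1.05 = +0.5 | +5.3 |
| 10% | 0 | 100% | +10.0 | 0 - 0.10/1.10 = -9.1 | 0.0 |
| 5% | 0 | 100% | +5.0 | 0 - 0.05/1.05 = -4.8 | 0.0 |
| 20% | 0 | 100% | +20.0 | 0 - 0.20/1.20 = -16.7 | 0.0 |
| 10% | 10% | 50% | 0.0 | 0.05/0.95 - 0.15/1.05 = -9.0 | -4.7 |
| 10% | 10% | 100% | 0.0 | 0 - 0.20/1.10 = -18.2 | -10.0 |

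Differences are in percentage points, THRIVE minus control. For a continuous outcome with no true effect, suppose conversion takes exactly the most extreme 10% of the THRIVE arm. The normal density at the cut-off is 0.1755, so moving those patients creates a spurious difference of 0.1755/0.90 + 0.1755/1.10 = 0.35 SD, and dropping them creates 0.1755/0.90 = 0.20 SD. A wrong grouping could therefore matter. By arm, the distortion is zero in every row, and with no conversions all three handlings agree.

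**Do the documents point to a wrong grouping?**

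1. *Labels.* Protocol at a Glance states that ETT/SGA is the control group, and the study table uses the control heading throughout. ETT alone appears in a short THRIVE checklist and is shorthand. It cannot affect a converted patient, who was randomised to THRIVE.
2. *Exposure.* Both protocol tables start THRIVE at 30 l/min before induction and raise it to 70 l/min at induction. Conversion comes up only at maintenance. A patient managed this way has already received THRIVE by the time conversion is considered, so non-THRIVE does not describe that patient even in ordinary as-treated language.
3. *Design.* The trial is randomised with two arms, and conversion is written as management within the THRIVE arm. Neither document mentions grouping by final device or excluding converted patients.
4. *Scope.* The SAP sentence is about patient characteristics, and gender is the one it names. If these are baseline characteristics, grouping by arm is the only sensible comparison, and the desaturation problem does not arise in that analysis. No supplied text names a proportion with SpO2 below 90% as an end-point.

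**The case for a change.** The strongest reply is that a natural reading is still an unwritten one. Converted patients carry the safety signal, the SAP contains the only definition of groups in either document, and a sentence on analysis by arm with a count of conversions would cost almost nothing. If characteristics is used loosely to include outcomes, the same undefined groups carry over to them.

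Part of this stands. The comparator is named inconsistently, the SAP is silent on the analysis set, and the number of and reasons for conversions are worth reporting in a study of THRIVE's safety. It does not show that the plan leads to a wrong analysis. The large figures need four things together: a binary end-point that the supplied text does not name, a grouping rule that it does not contain, assumed event rates, and conversion of all or many desaturating patients. On the last, the protocol asks only for a discussion with the surgeon. The SAP is also dated June 2020 and written in the past tense, so an added sentence would record what was done and could not pre-specify it.

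**Conclusion.** The concern does not call for a change. Followed on its natural reading, the plan compares the arms as randomised. Converted patients stay with THRIVE, and the regrouping distortion is zero at any conversion rate. The figures of -9.1 and -18.2 points are correct arithmetic for a grouping that the documents do not propose, so they measure a hypothetical misreading. The actual effect, if any, cannot be computed from the documents. The ETT label is a clerical slip, and the absent analysis-set sentence is a gap that a competent analyst fills correctly. Tabulating conversions belongs to ordinary reporting of the results.

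This rests on two assumptions: that the analysts used the randomisation list, as the design implies, and that THRIVE was started before induction as the protocol directs. Evidence that converted patients had in fact been regrouped or excluded would reopen the point; nothing in the documents suggests it.
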